11.0 TOXICITIES/SIDE EFFECTS

An adverse event is defined as any new untoward medical occurrence or worsening of a pre-existing medical condition in a clinical investigation subject administered study drug and that does not necessarily have a causal relationship with this treatment. An AE can therefore be any unfavorable or unintended sign, symptom, or disease temporally associated with the use of study drug/radiation or not considered related to the study drug/radiation. All AEs should be defined using the CTCAE v 4.0. All grade 1-5 adverse events should be reported and attributed.

The causal relationship to study drug is determined by the investigators and should be used to assess all AEs. The causal relationships are defined as follows:

- Related: there is a reasonable causal relationship between study drug/radiation administration and the AE.
- Not related: there is not a reasonable causal relationship between study drug/radiation administration and the AE.

The common understood meaning of “reasonable causal relationship” is that there is evidence to suggest a causal relationship.

11.1 Nivolumab Toxicity Management

For Nivolumab monotherapy, the safety profile is similar across various tumor types. There is no pattern in the incidence, severity, or causality of AEs to Nivolumab dose level. In phase 3 controlled studies, the safety profile of Nivolumab monotherapy is acceptable in the context of the observed clinical efficacy, and manageable using the below mentioned safety guidelines. Clinically relevant AEs typical of stimulation of the immune system were infrequent and manageable by delaying or stopping Nivolumab treatment and timely immunosuppressive therapy or other supportive care. For complete details please refer to the Investigator Brochure v.14 that accompanies this protocol.

11.1.1 Dose Delay Criteria

Because of the potential for clinically meaningful Nivolumab-related AEs requiring early recognition and prompt intervention, management algorithms have been developed for suspected AEs of selected categories. [See current Investigator Brochure]

Dose delay criteria apply for all drug-related adverse events. All study drugs must be delayed until treatment can resume.

Dose delay criteria apply for all drug-related AEs. Nivolumab must be delayed until treatment can resume.

Nivolumab administration should be delayed for the following:

Any Grade ≥ 2 non-skin, drug-related AE, with the following exceptions:

- Grade 2 drug-related fatigue or laboratory abnormalities do not require a treatment delay
- Any Grade 3 skin, drug-related AE

Any Grade ≥ 3 drug-related laboratory abnormality, with the following exceptions for lymphopenia, leukopenia, AST, ALT, total bilirubin, or asymptomatic amylase or lipase:

- Grade 3 lymphopenia or leukopenia does not require dose delay.
- If a subject has a baseline AST, ALT, or total bilirubin that is within normal limits, delay dosing for drug-related Grade ≥ 2 toxicity.
- If a subject has baseline AST, ALT, or total bilirubin within the Grade 1 toxicity range, delay dosing for drug-related Grade ≥ 3 toxicity.

Any AE, laboratory abnormality, or intercurrent illness which, in the judgment of the investigator, warrants delaying the dose of study medication.

11.1.2 Management Algorithms for Immuno-Oncology Agents

[figure not shown]
Immuno-Oncology (I-O) agents are associated with adverse events that can differ in severity and duration than adverse events caused by other therapeutic classes.

Nivolumab is considered an immune-oncology agent in this protocol. Early recognition and management of adverse events associated with immune-oncology agents may mitigate severe toxicity. Management algorithms have been developed to assist investigators in assessing and managing the following groups of adverse events:

- Gastrointestinal
- Renal
- Pulmonary
- Hepatic
- Endocrinopathies
- Skin
- Neurological

Hepatic Adverse Event Management Algorithm

Rule out non-inflammatory causes. If non-inflammatory cause, treat accordingly and continue I-O therapy. Consider imaging for obstruction.

[figure not shown]
Patients on IV steroids may be switched to an equivalent dose of oral corticosteroids (e.g. prednisone) at start of tapering or earlier, once sustained clinical improvement is observed. Lower bioavailability of oral corticosteroids should be taken into account when switching to the equivalent dose of oral corticosteroids.

*I-O therapy may be delayed rather than discontinued if AST/ALT = 8 x ULN and T.bili = 5 x ULN.

**The recommended starting dose for grade 4 hepatitis is 2 mg/kg/day methylprednisolone IV.

GI Adverse Event Management Algorithm

[figure not shown]
Rule out non-inflammatory causes. If non-inflammatory cause is identified, treat accordingly and continue I-O therapy. Opiates/narcotics may mask symptoms of perforation. Infliximab should not be used in cases of perforation or sepsis.

Patients on IV steroids may be switched to an equivalent dose of oral corticosteroids (e.g. prednisone) at start of tapering or earlier, once sustained clinical improvement is observed. Lower bioavailability of oral corticosteroids should be taken into account when switching to the equivalent dose of oral corticosteroids.

Renal Adverse Event Management Algorithm

[figure not shown]
Rule out non-inflammatory causes. If non-inflammatory cause, treat accordingly and continue I-O therapy

Patients on IV steroids may be switched to an equivalent dose of oral corticosteroids (e.g. prednisone) at start of tapering or earlier, once sustained clinical improvement is observed. Lower bioavailability of oral corticosteroids should be taken into account when switching to the equivalent dose of oral corticosteroids.

Pulmonary Adverse Event Management Algorithm

[figure not shown]
Rule out non-inflammatory causes. If non-inflammatory cause, treat accordingly and continue I-O therapy. Evaluate with imaging and pulmonary consultation.

Patients on IV steroids may be switched to an equivalent dose of oral corticosteroids (e.g. prednisone) at start of tapering or earlier, once sustained clinical improvement is observed. Lower bioavailability of oral corticosteroids should be taken into account when switching to the equivalent dose of oral corticosteroids.

Endocrinopathy Management Algorithm

[figure not shown]
Rule out non-inflammatory causes. If non-inflammatory cause, treat accordingly and continue I-O therapy. Consider visual field testing, endocrinology consultation, and imaging.

Patients on IV steroids may be switched to an equivalent dose of oral corticosteroids (e.g. prednisone) at start of tapering or earlier, once sustained clinical improvement is observed. Lower bioavailability of oral corticosteroids should be taken into account when switching to the equivalent dose of oral corticosteroids.

Skin Adverse Event Management Algorithm

Rule out non-inflammatory causes. If non-inflammatory cause, treat accordingly and continue I-O therapy.

[figure not shown]

Patients on IV steroids may be switched to an equivalent dose of oral corticosteroids (e.g. prednisone) at start of tapering or earlier, once sustained clinical improvement is observed. Lower bioavailability of oral corticosteroids should be taken into account when switching to the equivalent dose of oral corticosteroids.

*Refer to NCI CTCAE v4 for term-specific grading criteria.

Neurological Adverse Event Management Algorithm

Rule out non-inflammatory causes. If non-inflammatory cause, treat accordingly and continue I-O therapy.

Patients on IV steroids may be switched to an equivalent dose of oral corticosteroids (e.g. prednisone) at start of tapering or earlier, once sustained clinical improvement is observed. Lower bioavailability of oral corticosteroids should be taken into account when switching to the equivalent dose of oral corticosteroids.

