11.1.4 Criteria to Resume Treatment

Subjects may resume treatment with study drug when the drug-related AE(s) resolve to Grade \leq 1 or baseline value, with the following exceptions:

- Subjects may resume treatment in the presence of Grade 2 fatigue.
- Subjects who have not experienced Grade 3 drug-related skin AE may resume treatment in the presence of Grade 2 skin toxicity.
- Subjects with baseline Grade 1 AST/aLT or total bilirubin who require dose delays for reasons other than a 2-grade shift in AST/ALT or total bili may resume treatment in the presence of Grade 2 AST/ALT OR total bilirubin.
- Subjects with combined Grade 2 AST/ALT AND total bilirubin values meeting discontinuation parameters should have treatment permanently discontinued.
- Drug-related pulmonary toxicity, diarrhea, colitis, must have resolved to baseline before treatment is resumed.
- Drug-related endocrinopathies adequately controlled with only physiologic hormone replacement may resume treatment.

If the criteria to resume treatment are met, the subject should restart treatment at the next scheduled time-point per protocol. However, if the treatment is delayed past the next scheduled time-point per protocol, then next scheduled time-point will be delayed until dosing resumes.

Treatment may be delayed for up to a maximum of 6 weeks from the last dose; if treatment is delayed > 6 weeks, the subject must be permanently discontinued from study therapy, except as specified.

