13.2 Discontinuation Criteria for Nivolumab

Treatment should be permanently discontinued for the following:

- Any Grade 2 drug-related uveitis or eye pain or blurred vision that does not respond to topical therapy and does not improve to Grade 1 severity within re-treatment period OR requires systemic treatment.
- Any Grade 3 non-skin, drug related adverse event lasting > 7 days with the following exceptions for drug-related laboratory abnormalities, uveitis, pneumonitis, bronchospasm, neurologic toxicity, hypersensitivity reactions, and infusion reactions;
 - Grade 3 drug-related uveitis, pneumonitis, bronchospasm, neurologic toxicity, hypersensitivity reaction, or infusion reaction of any duration requires discontinuation.
 - Grade 3 drug-related laboratory abnormalities do not require treatment discontinuation except:
 - Grade 3 drug-related thrombocytopenia > 7 days or associated with bleeding requires discontinuation.

- Any drug related LFT abnormality that meets the following criteria require discontinuation;
 - AST or ALT > 8x ULN
 - Total bilirubin > 5x ULN
 - Concurrent AST or ALT > 3 x ULN and total bilirubin > 2 x ULN.
- Any grade 4 drug-related adverse event or laboratory abnormality, except for the following events which do NOT require discontinuation:
 - Isolated grade 4 electrolyte imbalances that are not associated with clinical sequelae and are corrected with supplementation/appropriate management within 72 hours of their onset.
 - Isolated grade 4 electrolyte imbalances that are not associated with clinical sequelae and are corrected with supplementation within 72 hours of their onset.
- Any dosing delays lasting > 6 weeks with the following exceptions:
 - Dosing delays to allow for prolonged steroid tapers to manage drug-related adverse events are allowed. Prior to reinitiating treatment in a subject with a dosing delay lasting > 6 weeks, the primary investigator must be consulted. Tumor assessments should continue as per protocol even if dosing is delayed.
 - Dosing delays > 6 weeks that occur for non-drug related reasons may be allowed if approved by the primary investigator. Prior to reinitiating treatment in a subject with a dosing delay lasting > 6 weeks, the primary investigator must be consulted. Tumor assessments should continue as per protocol even if dosing is delayed.

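### The hepatic footnote in 11.1.2 permits a nivolumab delay at combined liver values for which 13.2 requires permanent discontinuation, and no text says which prevails

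*Combined protocol and SAP*

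**What the plan says.** **Liver tests.** Three places in the combined protocol and SAP bear on the same patient.

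- Section 11.1.2, footnote to the hepatic algorithm: "I-O therapy may be delayed rather than discontinued if AST/ALT = 8 x ULN and T.bili = 5 x ULN". The algorithm itself is a figure that is not reproduced in the text available for review.
- Section 13.2, under the reasons for permanent discontinuation: "Any drug related LFT abnormality that meets the following criteria require discontinuation". Three criteria follow. The first is "AST or ALT > 8x ULN", the second is total bilirubin above 5 x ULN, and the third is "Concurrent AST or ALT > 3 x ULN and total bilirubin > 2 x ULN".
- Section 11.1.4, on resuming treatment: combined Grade 2 AST/ALT and bilirubin values that reach the discontinuation parameters lead to a permanent stop.

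**Amylase and lipase.** Section 11.1.1 delays nivolumab for drug-related laboratory abnormalities of Grade 3 or higher, "with the following exceptions for lymphopenia, leukopenia, AST, ALT, total bilirubin, or asymptomatic amylase or lipase". Bullets follow for lymphopenia/leukopenia and for the liver tests, but none for amylase or lipase. Section 13.2 stops treatment for "Any grade 4 drug-related adverse event or laboratory abnormality, except for the following events which do NOT require discontinuation". The two items listed as exceptions are nearly the same statement about isolated electrolyte imbalances.

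**Six-week limit.** Section 11.1.4: "Treatment may be delayed for up to a maximum of 6 weeks from the last dose", followed by a clause allowing for exceptions stated elsewhere. Section 13.2: "Any dosing delays lasting > 6 weeks with the following exceptions", with exceptions for steroid tapers and for approved delays unrelated to the drug.

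**The concern.** Nivolumab is the backbone drug in both arms, and these rules decide who stays on it. For a patient with combined transaminase and bilirubin elevation, one page allows treatment to be held with a view to restarting, and another requires it to end. The protocol treats this range as serious elsewhere: section 17.2.5 makes AST or ALT above 3 x ULN (above 5 x ULN with liver metastases) with bilirubin above 2 x ULN, and no other apparent explanation, reportable as potential drug-induced liver injury.

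Abnormal liver tests are foreseeable in this population. Patients with liver metastases may enter with AST/ALT up to 5 x ULN, and liver is a permitted SBRT site in Arm 2. An investigator who follows the footnote in good faith would breach 13.2.

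The amylase/lipase and six-week wording raises a lesser question: whether a site can tell what is required at all.

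**Working it through.** The plan states no figure to reproduce here. The check is to apply both liver rules to the same values and see where they disagree. Let A be AST or ALT and B be total bilirubin, both in multiples of ULN.

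**Inputs.**
- Stop rule (13.2): A > 8, or B > 5, or (A > 3 and B > 2).
- Delay permitted (11.1.2 footnote): A = 8 and B = 5 as printed. Because the sign may have been altered in typesetting, two further readings were tried: A ≤ 8 and B ≤ 5; and A ≥ 8 and B ≥ 5.

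**Step 1, as printed.** At A = 8, B = 5 the footnote permits a delay. In 13.2 the first criterion is not met (8 is not above 8), nor is the second (5 is not above 5). The third is met, since 8 > 3 and 5 > 2. Discontinuation is required, so the texts conflict.

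**Step 2, read as ≤.** Selected values:

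| A | B | Footnote permits delay | 13.2 liver criteria require stop | Conflict |
|---|---|---|---|---|
| 2 | 4 | yes | no | no |
| 6 | 1.5 | yes | no | no |
| 8 | 2 | yes | no | no |
| 3.5 | 2.5 | yes | yes | yes |
| 5 | 3 | yes | yes | yes |
| 8 | 2.1 | yes | yes | yes |
| 8 | 5 | yes | yes | yes |
| 8.1 | 1 | no | yes | no |

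On a grid of A from 0 to 12 and B from 0 to 8 in steps of 0.1, the conflicting points run from 3.1 to 8.0 for A and from 2.1 to 5.0 for B. The region is therefore 3 < A ≤ 8 with 2 < B ≤ 5. Every conflict in it arises through the third criterion alone.

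**Step 3, read as ≥.** Every combination that the footnote covers meets the 13.2 stop rule (for example 8 with 5, and 9 with 6), so all of them conflict.

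**Step 4, do other sections resolve it?** Section 13.2 makes no exception for the footnote, and the footnote makes none for the concurrent criterion. Section 11.1.4 supports 13.2, but only for combined Grade 2 values. Nothing states an order of precedence.

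**Step 5, amylase and lipase.** Being named in the 11.1.1 list does not fix the direction of the exception. For lymphopenia and leukopenia the bullet waives the delay at Grade 3 only. For liver tests that were normal at baseline, the bullet tightens the rule by delaying from Grade 2. With no amylase/lipase bullet, the rule is unstated. Section 13.2 is clear for Grade 4: no listed exception covers it.

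**Step 6, six-week limit.** Section 11.1.4 counts from the last dose. Section 13.2 gives no start. If, as an assumption, its delay runs from the missed due date under two-weekly dosing, the limit falls at 2 + 6 = 8 weeks after the last dose. A patient 7 weeks after the last dose (7 − 2 = 5 weeks past due) would then be over one limit and within the other. If 13.2 also counts from the last dose, there is no difference.

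**The case against.** The strongest reply is that the footnote only permits while 13.2 requires. A site that discontinues breaches neither text, and the algorithms are offered as an aid to investigators. That is correct, and it limits the conflict to sites that use the permission. It does not remove it, because the permission is printed without limit and nothing makes it subordinate to 13.2. The algorithm figure is not shown, so limiting words there cannot be excluded.

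A reader might infer several stronger things that the documents do not support.

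- **That the hold rules in 11.1 as a whole oppose 13.2.** They do not. The 11.1.1 delay triggers can be read as a lower tier, 11.1.4 points to 13.2 for combined Grade 2 values, and 11.1.5 agrees with 13.2 on Grade 3 and 4 infusion reactions.
- **That every patient in the 3-to-8 by 2-to-5 region receives conflicting instructions.** This holds only if the equals sign stands for ≤. As printed, the footnote covers one point.
- **That asymptomatic Grade 4 lipase is exempt from delay yet must end treatment.** Section 11.1.1 never states the exemption, so this is a missing rule and not a proven contradiction.
- **That the two six-week clocks differ by two weeks.** This depends on a start point that 13.2 does not give. The exception clause in 11.1.4 also allows the two sections to be read together.
- **That exposure will differ by arm because the trial is open label.** The rules are the same in both arms, and nothing in the documents shows differential use. Under the Follow-Up Phase in section 4.2, patients who stop for reasons other than progression keep their scheduled tumor assessments, so response is still captured.

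**Conclusion.** The contradiction is real and narrow. It lies between the hepatic footnote in 11.1.2 and the concurrent AST/ALT-plus-bilirubin criterion in 13.2, for drug-related abnormalities. It stands under all three readings of the sign: at one point as printed, over 3 < A ≤ 8 with 2 < B ≤ 5 if the sign means ≤, and at every combination covered if it means ≥. This rests on the printed footnote being complete without the missing figure.

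No frequency of combined elevation is given, so the number of patients affected among the planned 60 is unknown. The sample size and power figures are not touched. The reason to act is patient safety, together with the fact that a site can breach 13.2 by following another page of the same protocol.

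The amylase/lipase text and the six-week limit are unclear wording and warrant minor clarification only.

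**What to change.** Reconcile the 11.1.2 footnote, 11.1.4 and 13.2 so that each AST/ALT-plus-bilirubin combination has one outcome. State which section takes precedence, and print the intended comparison sign in the footnote. Which clinical rule stands is for the sponsor to decide.

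In the same amendment:

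- State the amylase/lipase rule that 11.1.1 announces, or remove the mention, and reconcile it with the Grade 4 rule in 13.2. Resolve the near-duplicate electrolyte item there.
- Give the same start point for the six-week limit in 11.1.4 and 13.2, and cross-refer to the exceptions.

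The cost is amendment wording. No procedures, visits or patients are added.

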11.1.3 Dose Modifications

Dose reductions or dose escalations are not permitted.

11.1.4 Criteria to Resume Treatment

Subjects may resume treatment with study drug when the drug-related AE(s) resolve to Grade \leq 1 or baseline value, with the following exceptions:

- Subjects may resume treatment in the presence of Grade 2 fatigue.
- Subjects who have not experienced Grade 3 drug-related skin AE may resume treatment in the presence of Grade 2 skin toxicity.
- Subjects with baseline Grade 1 AST/aLT or total bilirubin who require dose delays for reasons other than a 2-grade shift in AST/ALT or total bili may resume treatment in the presence of Grade 2 AST/ALT OR total bilirubin.
- Subjects with combined Grade 2 AST/ALT AND total bilirubin values meeting discontinuation parameters should have treatment permanently discontinued.
- Drug-related pulmonary toxicity, diarrhea, colitis, must have resolved to baseline before treatment is resumed.
- Drug-related endocrinopathies adequately controlled with only physiologic hormone replacement may resume treatment.

If the criteria to resume treatment are met, the subject should restart treatment at the next scheduled time-point per protocol. However, if the treatment is delayed past the next scheduled time-point per protocol, then next scheduled time-point will be delayed until dosing resumes.

Treatment may be delayed for up to a maximum of 6 weeks from the last dose; if treatment is delayed > 6 weeks, the subject must be permanently discontinued from study therapy, except as specified.

11.1.5 Treatment of Infusion Reaction

Since Nivolumab contains only human IgG protein sequences, it is unlikely to be immunogenic and induce infusion or hypersensitivity reactions. However, if such a reaction were to occur, it might manifest with fever, chills, rigors, headache, rash pruritus, arthralgias, blood pressure shifts, bronchospasms, or other symptoms. All Grade 3 or 5 infusion reactions should be reported within 24 hours to the primary investigator and reported as an SAE if criteria are met. Infusion reactions should be graded according to NCI CTCAE v 4.0 guidelines.

Treatment recommendations are provided below and may be modified based on local treatment standards and guidelines as appropriate:

For Grade 1 symptoms: (Mild reaction; infusion interruption not indicated; intervention not indicated)

Remain at bedside and monitor subject until recovery from symptoms. The following prophylactic premedications are recommended for future infusions: diphenhydramine 50 mg (or equivalent) and/or paracetamol 325 to 1000 mg (acetaminophen) at least 30 minutes before additional Nivolumab administrations.

For Grade 2 symptoms: (Moderate reaction requires therapy or infusion interruption but responds promptly to symptomatic treatment [e.g., antihistamines, non-steroidal anti-inflammatory drugs, narcotics, corticosteroids, bronchodilators, IV fluids]; prophylactic medications indicated for 24 hours).

Stop the Nivolumab infusion, begin an IV infusion of normal saline, and treat the subject with diphenhydramine 50 mg IV (or equivalent) and/or paracetamol 325 to 1000 mg (acetaminophen); remain at bedside and monitor subject until resolution of symptoms. Corticosteroid or bronchodilator therapy may also be administered as appropriate. If the infusion is interrupted, then restart the infusion at 50% of the original infusion rate when symptoms resolve; if no further complications ensue after 30 minutes, the rate may be increased to 100% of the original infusion rate. Monitor subject closely. If symptoms recur then no further Nivolumab will be administered at that visit. Administer diphenhydramine 50 mg IV, and remain at bedside and monitor the subject until resolution of symptoms. The amount of study drug infused must be recorded on the electronic case report form (eCRF). The following prophylactic premedications are recommended for future infusions: diphenhydramine 50 mg (or equivalent) and/or paracetamol 325 to 1000 mg (acetaminophen) should be administered at least 30 minutes before additional Nivolumab administrations. If necessary, corticosteroids (recommended dose: up to 25 mg of IV hydrocortisone or equivalent) may be used.

For Grade 3 or Grade 4 symptoms: (Severe reaction, Grade 3: prolonged [i.e., not rapidly responsive to symptomatic medication and/or brief interruption of infusion]; recurrence of symptoms following initial improvement; hospitalization indicated for other clinical sequelae [e.g., renal impairment, pulmonary infiltrates]). Grade 4: (life threatening; pressor or ventilatory support indicated).

Immediately discontinue infusion of Nivolumab. Begin an IV infusion of normal saline, and treat the subject as follows. Recommend bronchodilators, epinephrine 0.2 to 1 mg of a 1:1,000 solution for subcutaneous administration or 0.1 to 0.25 mg of a 1:10,000 solution injected slowly for IV administration, and/or diphenhydramine 50 mg IV with methylprednisolone 100 mg IV (or equivalent), as needed. Subject should be monitored until the investigator is comfortable that the symptoms will not recur. Nivolumab will be permanently discontinued. Investigators should follow their institutional guidelines for the treatment of anaphylaxis. Remain at bedside and monitor subject until recovery from symptoms. In the case of late-occurring hypersensitivity symptoms (e.g., appearance of a localized or generalized pruritus within 1 week after treatment), symptomatic treatment may be given (e.g., oral antihistamine, or corticosteroids).

